10.4 Expedited Reporting Requirements for IND/IDE Agents

10.41 Phase 1 and Early Phase 2 Studies: Expedited Reporting Requirements for Adverse Events that Occur on Studies under an IND/IDE within 30 Days of the Last Administration of the Investigational Agent/Intervention ^{1,2}

FDA REPORTING REQUIREMENTS FOR SERIOUS ADVERSE EVENTS (21 CFR Part 312)

NOTE: Investigators **MUST** immediately report to the sponsor **ANY** Serious Adverse Events, whether or not they are considered related to the investigational agent(s)/intervention (21 CFR 312.64)

An adverse event is considered serious if it results in **ANY** of the following outcomes:

- 1) Death
- 2) A life-threatening adverse event
- 3) An adverse event that results in inpatient hospitalization or prolongation of existing hospitalization for ≥ 24 hours
- 4) A persistent or significant incapacity or substantial disruption of the ability to conduct normal life functions
- 5) A congenital anomaly/birth defect.
- 6) Important Medical Events (IME) that may not result in death, be life threatening, or require hospitalization may be considered serious when, based upon medical judgment, they may jeopardize the patient or subject and may require medical or surgical intervention to prevent one of the outcomes listed in this definition. (FDA, 21 CFR 312.32; ICH E2A and ICH E6).

ALL SERIOUS adverse events that meet the above criteria **MUST** be immediately reported to the sponsor within the timeframes detailed in the table below.

Hospitalization	Grade 1 and Grade 2 Timeframes	Grade 3-5 Timeframes
Resulting in Hospitalization ≥24 hrs	7 Calendar Days	24-Hour 3 Calendar Days
Not resulting in Hospitalization ≥24 hrs	Not required	

Expedited AE reporting timelines are defined as:

- "24-Hour; 3 Calendar Days" - The AE must initially be reported within 24 hours of learning of the AE, followed by a complete expedited report within 3 calendar days of the initial 24-hour report.
- "7 Calendar Days" - A complete expedited report on the AE must be submitted within 7 calendar days of learning of the AE.

¹Serious adverse events that occur more than 30 days after the last administration of investigational agent/intervention and have an attribution of possible, probable, or definite require reporting as follows:

Expedited 24-hour notification followed by complete report within 3 calendar days for:

- All Grade 3, 4, and Grade 5 AEs

Expedited 7 calendar day reports for:

- Grade 2 AEs resulting in hospitalization or prolongation of hospitalization

² For studies using PET or SPECT IND agents, the AE reporting period is limited to 10 radioactive half-lives, rounded UP to the nearest whole day, after the agent/intervention was last administered. Footnote "1" above applies after this reporting period.

Effective Date: May 5, 2011

NOTE: Refer to Section 10.32 for exceptions to Expedited Reporting

10.42 General reporting instructions

The Mayo IND Coordinator will assist the sponsor-investigator in the processing of expedited adverse events and forwarding of suspected unexpected serious adverse reactions (SUSARs) to the FDA and IRB.

Use Mayo Expedited Event Report form

<http://livelcycle2.mayo.edu/workspace/?startEndpoint=MC4158->

[56/Processes/MC4158-56-Process.MC4158-56](#) for investigational agents or commercial/investigational agents on the same arm.

Submit to Taiho Oncology Inc. Pharmacovigilance contact information for IIT sites to report SAEs (email to #1 preferred):

1. [REDACTED] (please note the underscore between [REDACTED] and [REDACTED])
2. FAX: [REDACTED]
3. Hotline phone: [REDACTED] (phone number is only to ask questions, not to report SAEs)

For commercial agents:

Submit form MedWatch 3500A to the FDA, [name], by fax at [name] or online at

<http://www.fda.gov/Safety/MedWatch/HowToReport/default.htm>.

10.43 Reporting of re-occurring SAEs

ALL SERIOUS adverse events that meet the criteria outlined in table 10.41 MUST be immediately reported to the sponsor within the timeframes detailed in the corresponding table. This reporting includes, but is not limited to SAEs that re-occur again after resolution.

10.5 Other Required Reporting

10.51 Unanticipated Problems Involving Risks to Subjects or Others (UPIRTSOS)

Unanticipated Problems Involving Risks to Subjects or Others (UPIRTSOS) in general, include any incident, experience, or outcome that meets **all** of the following criteria:

1. Unexpected (in terms of nature, severity, or frequency) given (a) the research procedures that are described in the protocol-related documents, such as the IRB-approved research protocol and informed consent document; and (b) the characteristics of the subject population being studied;
2. Related or possibly related to participation in the research (in this guidance document, possibly related means there is a reasonable possibility that the incident, experience, or outcome may have been caused by the procedures involved in the research); and
3. Suggests that the research places subjects or others at a greater risk of harm (including physical, psychological, economic, or social harm) than was previously known or recognized.

Some unanticipated problems involve social or economic harm instead of the physical or psychological harm associated with adverse events. In other cases, unanticipated problems place subjects or others at increased *risk* of harm, but no harm occurs.

Note: If there is no language in the protocol indicating that pregnancy is not considered an adverse experience for this trial, and if the consent form does not indicate that subjects should not get pregnant/impregnate others, then any pregnancy in a subject/patient or a male patient's partner (spontaneously reported) which occurs during the study or within 120 days of completing the study should be reported as a UPIRTSO.

Mayo Clinic Cancer Center (MCCC) Institutions:

If the event meets the criteria for IRB submission as a Reportable Event/UPIRTSO, provide the appropriate documentation and use the Mayo Clinic Cancer Center Expedited Event Report form

<http://livelcycle2.mayo.edu/workspace/?startEndpoint=MC4158-56/Processes/MC4158-56-Process.MC4158-56>, to submit to

[contact]. The Mayo Regulatory Affairs Office will review and process the submission to the Mayo Clinic IRB.

10.52 Death

Note: A death on study requires both routine and expedited reporting regardless of causality, unless as noted below. Attribution to treatment or other cause must be provided.

Any death occurring within 30 days of the last dose, regardless of attribution to an agent/intervention under an IND/IDE requires expedited reporting within 24-hours.

Any death occurring greater than 30 days with an attribution of possible, probable, or definite to an agent/intervention under an IND/IDE requires expedited reporting within 24-hours.

Reportable categories of Death

- Death attributable to a CTCAE term.
- Death Neonatal: A disorder characterized by cessation of life during the first 28 days of life.
- Death NOS: A cessation of life that cannot be attributed to a CTCAE term associated with Grade 5.
- Sudden death NOS: A sudden (defined as instant or within one hour of the onset of symptoms) or an unobserved cessation of life that cannot be attributed to a CTCAE term associated with Grade 5.
- Death due to progressive disease should be reported as **Grade 5 “Neoplasms benign, malignant and unspecified (including cysts and polyps) – Other (Progressive Disease)”** under the system organ class (SOC) of the same name. Evidence that the death was a manifestation of underlying disease (e.g., radiological changes suggesting tumor growth or progression: clinical deterioration associated with a disease process) should be submitted.

Per NIH OBA Appendix M, should a patient die during the study or study follow-up, no matter what the cause, the study doctor will ask the patient's family for permission to perform an autopsy. If permission is granted, a copy of the autopsy report will be sent to the sponsor after all identifying information has been removed. An autopsy will help the researchers learn

more about the safety and efficacy of the treatment. Patients should advise their families about their wishes regarding autopsy.

10.53 Secondary Malignancy

- A **secondary malignancy** is a cancer caused by treatment for a previous malignancy (e.g., treatment with investigational agent/intervention, radiation or chemotherapy). A secondary malignancy is not considered a metastasis of the initial neoplasm.
- All secondary malignancies that occur following treatment with an agent under an IND/IDE will be reported. Three options are available to describe the event:
 - Leukemia secondary to oncology chemotherapy (e.g., Acute Myelocytic Leukemia [AML])
 - Myelodysplastic syndrome (MDS)
 - Treatment-related secondary malignancy
- Any malignancy possibly related to cancer treatment (including AML/MDS) should also be reported via the routine reporting mechanisms outlined in each protocol.

10.54 Second Malignancy

A second malignancy is one unrelated to the treatment of a prior malignancy (and is NOT a metastasis from the initial malignancy). Second malignancies require ONLY routine reporting unless otherwise specified.

10.55 Pregnancy, Fetal Death, and Death Neonatal

If a patient becomes pregnant while in the study, the study treatment must be immediately discontinued. Pregnancy information for a female patient should be reported **within 24 hours** from the time the investigator first becomes aware of a pregnancy or its outcome. This should be performed by completing a Pregnancy Form and faxing it to Taiho Pharmacovigilance or designee.

New and/or corrected information regarding the pregnancy obtained after submitting the initial Pregnancy Form must be submitted by faxing an updated Pregnancy Form to Taiho Pharmacovigilance or designee.

If outcome of the pregnancy is a stillbirth, congenital anomaly/birth defect, or a serious event in the mother, report as an SAE to Taiho Pharmacovigilance or designee.

If a female subject (or female partner of a male subject) taking investigational product becomes pregnant, the subject taking should notify the Investigator, and the pregnant female should be advised to call her healthcare provider immediately. The patient should have appropriate follow-up as deemed necessary by her physician.

NOTE: When submitting Mayo Expedited Adverse Event Report reports for “Pregnancy”, “Pregnancy loss”, or “Neonatal loss”, the potential risk of exposure of the fetus to the investigational agent(s) or chemotherapy agent(s) should be documented in the “Description of Event” section. Include any available medical documentation. Include this form:

http://ctep.cancer.gov/protocolDevelopment/electronic_applications/docs/PregnancyReportFormUpdated.pdf

10.551 Pregnancy

Pregnancy should be reported in an expedited manner as **Grade 3** “**Pregnancy, puerperium and perinatal conditions - Other (pregnancy)**” under the Pregnancy, puerperium and perinatal conditions SOC. Pregnancy should be followed until the outcome is known.

10.552 Fetal Death

Fetal death is defined in CTCAE as “A disorder characterized by death in utero; failure of the product of conception to show evidence of respiration, heartbeat, or definite movement of a voluntary muscle after expulsion from the uterus, without possibility of resuscitation.”

Any fetal death should be reported expeditiously, as **Grade 4** “**Pregnancy, puerperium and perinatal conditions - Other (pregnancy loss)**” under the Pregnancy, puerperium and perinatal conditions SOC.

10.553 Death Neonatal

Neonatal death, defined in CTCAE as “A disorder characterized by cessation of life occurring during the first 28 days of life” that is felt by the investigator to be at least possibly due to the investigational agent/intervention, should be reported expeditiously.

A neonatal death should be reported expeditiously as **Grade 4** “**General disorders and administration - Other (neonatal loss)**” under the General disorders and administration SOC.

10.6 Required Routine Reporting

10.61 Baseline and Adverse Events Evaluations

Pretreatment symptoms/conditions to be graded at baseline and adverse events to be graded at each evaluation.

Grading is per CTCAE v4.0 **unless** alternate grading is indicated in the table below:

CTCAE System/Organ/Class (SOC)	Adverse event/Symptoms	Baseline	Each evaluation
Blood and lymphatic system disorders	Anemia	X	X
Gastrointestinal Disorders	Abdominal Pain	X	X
	Baseline # of stools	X	
	Diarrhea		X
	Nausea	X	X
	Vomiting	X	X
General disorders	Fatigue	X	X
Investigations	Neutrophil count decreased	X	X
	Platelet count decreased	X	X
Metabolism and nutrition disorders	Anorexia	X	X

10.62 All other AEs

Submit via appropriate MCCC Case Report Forms (i.e., paper or electronic, as applicable) the following AEs experienced by a patient and not specified in Section 10.6:

10.621 Grade 2 AEs deemed *possibly, probably, or definitely* related to the study treatment or procedure.

10.622 Grade 3 and 4 AEs regardless of attribution to the study treatment or procedure.

10.623 Grade 5 AEs (Deaths)

10.6231 Any death within 30 days of the patient's last study treatment or procedure regardless of attribution to the study treatment or procedure.

10.6232 Any death more than 30 days after the patient's last study treatment or procedure that is felt to be at least possibly treatment related must also be submitted as a Grade 5 AE, with a CTCAE type and attribution assigned.

10.7 Late Occurring Adverse Events

Refer to the instructions in the Forms Packet (or electronic data entry screens, as applicable) regarding the submission of late occurring AEs following completion of the Active Monitoring Phase (i.e., compliance with Test Schedule in Section 4.0).

10.8 Taiho Oncology Additional Event Reporting Instructions

Serious adverse events must be reported to Taiho Pharmacovigilance or designee **within 24 hours** from the time the investigator first becomes aware of the SAE. Comprehensive information available at the time of initial reporting (including narrative description, medical history and concomitant medications) needs to be provided with careful consideration regarding causality and serious criteria.

After the initial SAE notification to Taiho Pharmacovigilance or designee, follow-up SAE information will be submitted each time that important follow-up information (e.g., diagnosis, outcome, causality assessment, results of specific investigations) becomes available.

All SAEs **within** the follow-up window (e.g., within 30 days after the last dose of study drug or until the start of new antitumor therapy, whichever is earlier) established in the protocol will be reported to Taiho Pharmacovigilance or designee.

If serious medical occurrences including deaths **outside** the follow-up window established by the protocol are reported to or observed by the investigator that he/she believes are related to the administration of the investigational product, it is the investigator's responsibility to report this occurrence to Taiho Pharmacovigilance or designee.

10.81 Reporting of Deaths

All deaths occurring through the 30-day follow-up period must be reported to Taiho Pharmacovigilance or designee **within 24 hours**.

1. Death due to disease progression:

Disease progression (radiologic or clinical) with the outcome of death will not be reported as an SAE. However, relevant signs, symptoms and complications of disease progression (radiologic or clinical) must be reported as an AE or SAE if it meets the serious criteria. It should be indicated that the signs, symptoms and complications are related to disease progression.

2. Death due to other causes:

Deaths due to reasons other than disease progression must be reported as an SAE.

Death is not an acceptable AE/SAE term. Death is an outcome of an SAE.

When reporting a death, the investigator will be required to identify which of the following best describes the category of death:

- Toxicity for study drugs
- Radiologic disease progression
- Clinical disease progression
- Other causes

10.82 Disease Progression

How to report events related to non-fatal disease progression:

- a. Disease progression is not an acceptable AE term. In cases of non-fatal disease progression, the relevant signs, symptoms and complications should be reported as an AE unless they meet the serious criteria. If any of the signs, symptoms and complications meets any of the serious criteria, they should be reported as an SAE. In both cases it should be indicated whether the signs, symptoms and complications are related to disease progression.
- b. Radiologic disease progression without relevant signs, symptoms and complications will **not** be reported as an AE or SAE.

10.83 Pregnancy

If a patient becomes pregnant while in the study, the study treatment must be immediately discontinued. Pregnancy information for a female patient should be reported **within 24 hours** from the time the investigator first becomes aware of a pregnancy or its outcome. This should be performed by completing a Pregnancy Form and faxing it to Taiho Pharmacovigilance or designee.

New and/or corrected information regarding the pregnancy obtained after submitting the initial Pregnancy Form must be submitted by faxing an updated Pregnancy Form to Taiho Pharmacovigilance or designee.

If outcome of the pregnancy is a stillbirth, congenital anomaly/birth defect, or a serious event in the mother, report as an SAE to Taiho Pharmacovigilance or designee.

10.84 Medication Errors

A **medication error** is defined as any accidental incorrect administration of a medicinal product. The error may be related to the administration of a wrong medication, nature of the medication, route of administration, dosage or

frequency of the treatment as specified in this protocol (including omission of one or more administrations).

- Medication errors with study drugs and concomitant medication treatment will not be reported unless they result in an AE.
- Medication errors with study drugs that result in an overdose will be reported as an AE.
- Medication errors with study drugs that do not result in an AE should be handled as follows:
 - If it results in the omission of an administration, an incorrect dose (relative to that specified in this protocol), or the administration of more than the prescribed dose (but does not meet the overdose criteria), it will be identified through the recording of study drug accountability data in the CRF and does not need to be reported as an AE.
 - If it results in an overdose, incorrect route of administration, or administration of an incorrect study drug, it will be reported as an AE.

Based on the above criteria, medication errors that are captured as an AE on the CRF should be reported to Taiho Pharmacovigilance or designee **within 24 hours** from the time the investigator first becomes aware of its occurrence following the same process as described for the SAEs even if it does not meet any of the criteria of an SAE.

10.85 Overdose

An overdose with FTD/TPI (TAS-102) for this clinical trial is defined as:

- Taking a dose beyond the recommended dose in 1 day or beyond the recommended total dose in each cycle.

An accidental or intentional overdose with FTD/TPI (TAS-102) regardless of whether it is associated with an AE (even if not fulfilling a seriousness criterion) is to be captured as an AE on the CRF and reported to Taiho Pharmacovigilance or designee **within 24 hours** from the time the investigator first becomes aware of its occurrence following the same process as described for the SAEs.

There is no known antidote available in case of FTD/TPI (TAS-102) overdose. Overdose should be managed aggressively with close monitoring and administration of prophylactic and symptomatic therapies to prevent or correct potential side effects.

An accidental or intentional overdose for concomitant medication should only be reported if it is associated with an AE.

To Report to Taiho Pharmacovigilance: [REDACTED]

11.0 Treatment Evaluation

NOTE: This study uses protocol RECIST v1.1 template dated 2/16/2011. See the footnote for the table regarding measureable disease in Section 11.44, as it pertains to data collection and analysis.

Response and progression will be evaluated in this study using the new international criteria proposed by the revised Response Evaluation Criteria in Solid Tumors (RECIST) guidelines (version 1.1) (*Eisenhauer et al*). Changes in the largest diameter (unidimensional measurement) of the tumor lesions and the short axis measurements in the case of lymph nodes are used in the RECIST guideline.

11.1 Schedule of Evaluations

For the purposes of this study, patients should be reevaluated every 8 weeks. In addition to a baseline scan, confirmatory scans should also be obtained 8 weeks following initial documentation of objective response.

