1.4 Study Design

This is the single arm phase II trial to assess the efficacy of FTD/TPI in advanced, refractory BTCs. The primary end point of this study is 16-week progression-free survival. If 30% of patients remain progression-free at 16-weeks, this trial will be considered a success warranting bigger trials. We will accrue 25 evaluable patients using a single stage design. The total sample size of this study is 28 to account for 3 possible non-evaluable subjects.

Patient will receive FTD/TPI at the dose of 35 mg/m² on Days 1-5 and 8-12 of 28-day cycle. Patient will receive treatment until disease progression or unacceptable toxicities. Patients will undergo restaging scans every 2 cycles. Subjects will be monitored for adverse events from the beginning of the study drug to 28 days after the last dose. We will collect blood samples for determination of cell free DNA and circulating tumor cells at baseline, after 2 cycles and at progression.

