4.0 Study Schedules

4.1 Test schedule

Tests and Procedures	Screening prior to registration	Active Treatment			End of Treatment	
		D1 of each cycle	D8 of Cycle 1 only	Every 2 cycles	End of Treatment	Safety follow up: 30 days post treatment
window		±7 days	±3 days	±7 days	±7 days	±7 days
History and exam, Wt, PS	X	X	X		X	X
Height	X					
Adverse event assessment	X	X	X		X	X
Pregnancy test ¹	X					
Hematology: CBC with differential	X	X	X		X	X
Chemistry ²	X	X	X		X	X
CA19-9 ³		X		X ⁴	X	
Tumor imaging - CT (chest, abdomen, pelvis) or CT (chest) and MRI (abdomen, pelvis)	X ⁵			X ⁶	X	
Research blood specimens ^{7,R}		X			X	
Patient Medication Diary (Appendix II) ⁸		X				

Cycle = 28 days; R=Research funded

¹ For persons of childbearing potential only. Must be done ≤7 days prior to registration.

² Chemistry: Na, K, albumin, AST, ALT, alkaline phosphatase, total and direct bilirubin, creatinine

³ Baseline prior to Cycle 1, Day 1, then every two cycles or as clinically indicated

⁴ To be performed ≤7 days prior to planned Day 1 of odd numbered cycles (Cycle 3, 5, 7 etc) or as clinically indicated

⁵ Can be performed ≤28 days prior registration

⁶ To be performed ≤7 days prior to planned Day 1 of odd numbered cycles (Cycle 3, 5, 7 etc) or as clinically indicated

⁷ Research blood specimens to be collected on Cycle 1 Day 1 (or any time between registration and Cycle 1 Day 1), Cycle 3 Day 1 and end of treatment (see [Section 14.0](#))

⁸ The diary must begin the day the patient starts taking the medication and must be completed per protocol and returned to the treating institution

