8.3 Dose Modifications at the Time of Retreatment (Beginning of new cycle)

8.31 The dose modification guidelines for FTD/TPI (TAS-102) for non-specified adverse events on **Day 1** of each cycle of the treatment is mentioned below:

CTCAE Adverse Events ¹	Action for FTD/TPI (TAS-102)
Grade 1 or 2	Treat as scheduled
Grade 3 or 4	Delay Treatment until resolve to \leq Grade 2. Reduce the dose by one dose level.

¹ Except for alopecia, clinically insignificant laboratory abnormalities, and inadequately treated nausea, vomiting and diarrhea.

8.32 The dose modification guidelines for FTD/TPI (TAS-102) for specified adverse events on **Day 1** of each cycle of the treatment is mentioned below:

CTCAE { Adverse Events	Action for FTD/TPI (TAS-102)
Neutrophil count decreased $<1,500/\text{mm}^3$	Delay treatment by 1 week Reduce dose by one dose level for next treatment only if febrile neutropenia or uncomplicated Grade 4 neutropenia occurs that requires more than one week delay in start of next cycle
Platelet count decreased $<75,000/\text{mm}^3$	Delay treatment by 1 week Reduce dose by one dose level for next treatment only if Grade 4 thrombocytopenia occurs that requires more than one week delay in start of next cycle

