13.8 Patient removal from study

Patients may be removed from treatment on this study for any of the following reasons:

- Progression of disease
- Noncompliance with study procedures
- Patient's request to withdraw from the study or refusal of further therapy
- Unacceptable adverse events: A patient may be removed from the study for any complication of treatment that the investigator feels is life threatening
- Investigator discretion
- Dose delay >28 days for treatment related AE NOTE: If a patient has clinical benefit from the study treatment, patient may continue on study at investigator discretion

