15.19 Nursing Guidelines

- 15.191 Instruct Patients to take FTD/TPI (TAS-102) within 1 hour after morning or evening meal with a glass of water. Patients will not make up for a missed dose. If a patient vomits after taking the study medication, the dose should not be replaced.
- 15.192 Patients may experience fatigue. Instruct patients in energy conserving lifestyle.
- 15.193 GI side effects are common, including nausea, decreased appetite, diarrhea, vomiting, and abdominal pain.
- 15.194 Cytopenias are common. Monitor CBC w/diff and instruct patients to report any signs or symptoms of infection and/or unusual bruising or bleeding to the study team.
- 15.195 Rarely Pulmonary embolism has been reported with this agent. Instruct patient to report any shortness of breath or chest pain to study team and/or seek out emergency medical attention.
- 15.196 Although uncommon, warn patients of the possibility of alopecia.

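### Scans are set every 8 calendar weeks in one place and every 2 cycles in others; once cycles are delayed for toxicity the two rules part, and the plan does not say which governs

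*Combined protocol and SAP*

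**What the plan says.** Tumor assessment is timed in two ways.

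- **By calendar.** Section 11.1: "patients should be reevaluated every 8 weeks".
- **By cycle.** Section 1.4: "Patients will undergo restaging scans every 2 cycles". Section 4.1, footnote 6, on imaging: "To be performed ≤7 days prior to planned Day 1 of odd numbered cycles", naming Cycles 3, 5 and 7, or as clinically indicated. The table column that carries this footnote also shows a window of ±7 days.

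A cycle is nominally 28 days, but its start can slip. For low neutrophils or platelets on Day 1, Section 8.32 says "Delay treatment by 1 week", and it foresees an event that "requires more than one week delay in start of next cycle". Section 8.31 delays Day 1 for other Grade 3 or 4 events until they settle. Section 13.8 lists "Dose delay >28 days for treatment related AE" as a possible reason for removal from treatment, with continuation allowed at discretion, so shorter delays are expected to be tolerated.

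The endpoints run on the calendar. Section 16.21 counts a success at 16 weeks from registration. Section 16.3 equates 16 weeks on study with having had the second scan. Section 16.322 estimates PFS from study entry by Kaplan-Meier and makes no provision for uneven scan intervals.

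**The concern.** The two rules coincide only if every cycle lasts 28 days. After a delay, a patient scanned by the cycle rule is assessed later than one scanned by the calendar rule, and nothing says which is correct or that scans keep their dates when dosing slips. Delays come from toxicity, so under the cycle rule the timing of assessment depends on how the patient tolerates the drug.

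Two results are exposed. Progression found by scan is dated no earlier than the scan, so recorded PFS can lengthen for the same disease course. And a patient may have no scan by week 16, so that a progression before the landmark is first seen after it and may be counted as a success. The trial has a single arm judged against a fixed 10%, so no control arm absorbs the shift.

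**Working it through.** **1. The plan's own figures.** With success declared at 6 or more of 25, P(X ≥ 6) for X ~ Binomial(25, p) is 0.0334, 0.1615, 0.3833, 0.6217 and 0.8065 at p = 0.10, 0.15, 0.20, 0.25 and 0.30. Section 16.24 gives 0.033, 0.160, 0.383, 0.622 and 0.807. The table stands, apart from a trivial third-decimal difference at 0.15.

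**2. Scan windows under footnote 6 read alone.** Take day 0 as both registration and first dose. Undelayed, Cycle 3 Day 1 is day 2 × 28 = 56 and Cycle 5 Day 1 is day 4 × 28 = 112. The window is the 7 days up to that day, and each week of accumulated delay adds 7 days.

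| Accumulated delay | Scan 1 window (days) | Scan 2 window (days) |
|---|---|---|
| none | 49–56 | 105–112 |
| 1 week | 56–63 | 112–119 |
| 2 weeks | 63–70 | 119–126 |

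For scan 1 the relevant delay is the one before Cycle 2. For scan 2 it is the sum of delays before Cycles 2, 3 and 4. With one week of delay, day 56 or day 112 still meets both rules. With two weeks, no day in the window is at or before week 8 or week 16. If the ±7 days is instead applied to the calendar target, day 112 + 7 = 119 is in window, but it is still after the landmark.

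**3. Effect on recorded PFS.** Assume exponential PFS with progression seen only at scans every L weeks. With hazard λ = −ln(p16)/16, where p16 is the true 16-week rate, mean recorded PFS = L / (1 − e^(−λL)).

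| True 16-week rate | True mean | L = 8 | L = 9 | L = 10 |
|---|---|---|---|---|
| 10% | 6.9 | 11.7 | 12.4 | 13.1 |
| 30% | 13.3 | 17.7 | 18.3 | 18.9 |

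(All in weeks.) Each extra week of interval adds about 0.7 week at 10% and 0.6 week at 30%.

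The median behaves differently. On the same model the recorded median at 10% is 8, 9 and 10 weeks for L = 8, 9 and 10. At 30% it is 16, 18 and 10 weeks: it falls at L = 10 because just over half of patients (1 − 0.471 = 0.529) have progressed by week 10.

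**4. Effect on the 16-week endpoint (illustration).** Suppose a share f of patients have scan 2 after week 16, and a share q of their progressions between weeks 8 and 16 are detectable only by that scan. The apparent rate is p + f·q·(S8 − p), where S8 = √p is the proportion progression-free at week 8. At p = 0.10, S8 = 0.316.

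| f | Apparent rate, q = 1 | P(≥6/25), q = 1 | P(≥6/25), q = 0.5 |
|---|---|---|---|
| 0 | 10.0% | 0.033 | 0.033 |
| 10% | 12.2% | 0.075 | 0.051 |
| 20% | 14.3% | 0.138 | 0.075 |
| 30% | 16.5% | 0.220 | 0.103 |

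The documents give neither f nor q. The ranges are assumed, and q = 1 is the upper end.

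**The case against.** The case for leaving this as a minor wording matter has real content.

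- **Not every delay moves a scan.** A reader might infer that each hematologic delay stretches the interval. The documents do not support that. The scan is done before planned Day 1, while the Section 8.32 delay is called on Day 1, so a delay at Cycle 3 or Cycle 5 Day 1 usually follows a scan already done. Holds within a cycle under Section 8.22 do not lengthen it, and one week can be absorbed. Planned Day 1 might even mean the originally scheduled date. The text does not say so, and that is itself part of the ambiguity.
- **A scan-date shift is not a shift in median PFS.** Moving one patient's scan from week 8 to week 9 or 10 is 1/8 = 12.5% or 2/8 = 25% later, and a reader might carry those percentages over to the median. They do not carry over. At a true rate of 10%, 68% have progressed by week 8, so the recorded median leaves week 8 only if more than about 27% of patients have a delayed first scan (1 − 0.5/0.684). At 30%, the median can move either way, as shown above.
- **Neutropenia rates are not delay rates.** Section 15.19 notes "Cytopenias are common", and Table 1 in Section 1.2 gives neutropenia in 67%, Grade 3-4 in 38%. Those come from colorectal cancer and are not rates of a low count on Day 1. They make delays plausible without measuring them, and Section 8.2 allows G-CSF.
- **Other routes to progression limit the bias.** Deaths are dated exactly, Section 11.45 counts symptomatic deterioration as progression, and Section 4.1 allows scans when clinically indicated.
- **The landmark is already on the calendar.** True, but a calendar endpoint read from cycle-timed scans is exactly the mismatch at issue.

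These points limit the size and reach of the effect. None says which schedule governs.

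**Conclusion.** The conflict is real and the documents do not resolve it. Under the cycle rule, assessment timing can depend on toxicity, with certainty only from two weeks of accumulated delay under footnote 6 read alone. Recorded PFS can then lengthen, by about 0.6 to 0.7 week in the mean per extra week of interval on the exponential, scan-only model, and progressions before week 16 can escape the landmark.

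The overall size is uncertain because no delay rate is given. A reader might conclude from the illustration that the false-positive rate does exceed the nominal 0.05. The documents do not establish that: it depends on an assumed share of late second scans and on how many progressions only a scan would reveal. The sample size and power arithmetic are not in error. The change is worth making because it removes a toxicity-dependent source of bias at little cost.

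**What to change.** Make Section 11.1 govern. In Section 1.4 and in footnote 6 of Section 4.1, replace the cycle-based timing with scans every 8 calendar weeks counted from registration, regardless of dose delays or holds, and name the same anchor in Section 11.1. Registration is the right origin because Section 16.21 counts the 16 weeks from it. Section 6.6 allows up to 28 days between registration and treatment start, so counting from first dose could still put scan 2 up to 4 weeks after the landmark.

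State one 7-day window: Section 4.1 now carries both up to 7 days before and ±7 days. A window that closes on the target day keeps scan 2 at or before week 16; a ±7-day window does not.

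Dosing rules are untouched. The cost is wording and about the same number of scans. After a delay, or when treatment starts some time after registration, the scan may not coincide with a cycle start, the CA19-9 test or the Cycle 3 Day 1 research blood draw. At the 28-day limit, scan 1 would fall 56 − 28 = 28 days after first dose.
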